### 5.6.3.2. Vital Signs

Continuous vital sign parameters including pulse, blood pressure (systolic and diastolic) will be summarized at each assessment time point. Change from baseline will be summarized. Descriptive statistics (mean, standard deviation, median, minimum and maximum) will be presented.

Incidence of treatment-emergent abnormal vital signs during intervention, as defined in Table 6, will be summarized for participants who had a baseline assessment and at least 1 postbaseline assessment for that vital sign.

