**Footnotes:**

- A final follow-up visit (ie, Week 20) will be conducted approximately 4 weeks after the last administration of study intervention.
- Participants who terminate study intervention early should return for an early termination visit as soon as possible after discontinuing study intervention and return for the final follow-up visit approximately 4 weeks after their last administration of study intervention.
- At all visits where study intervention will be dispensed, all study procedures and evaluations are to be completed before study intervention is dispensed.
- Must be signed before any study-related activity. Optional biomarker substudies include skin biopsy and/or ex vivo whole blood cytokine release assay sample collections.
- Minimum criteria for the availability of documentation supporting the eligibility criteria are described in Section 5.1 Inclusion Criteria and Section 5.2, Exclusion Criteria. Check clinical status again before first administration of study intervention at Week 0.
- Chest radiograph must be taken within 12 weeks prior to first administration of study intervention.

- g. Interferon gamma release assay testing includes either QuantiFERON-TB® or T-SPOT®TB. A tuberculin skin test in addition to IGRA testing maybe also used to screen for latent TB if preferred by local health authorities, or at the request of the investigator based on their judgment that both tests are clinically indicated to evaluate a participant at high risk for latent TB.
- h. Women of childbearing potential must have a negative serum pregnancy test result during screening and a negative urine pregnancy test at all other required visits prior to dispensing study intervention. The urine assessment can be performed any time during the study visit including prior to the PRO collection.
- i. To confirm postmenopausal status in women, if applicable (refer to Section 10.5, Appendix 5: Contraceptive and Barrier Guidance for more details).
- j. Participants will be instructed to complete a daily dosing diary to record the date and time of the following: when they last consumed food or caloric drinks before the administration of study intervention, when they take the study intervention, and when they first consumed food or caloric drinks after the administration of study intervention. Sites will review the diary entries for completeness and to ensure the participants are following the dosing instructions.

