##### **Type of Participant and Disease Characteristics**

2. has a diagnosis of plaque psoriasis, with or without psoriatic arthritis, for at least 26 weeks prior to the first administration of study intervention.

3. has a total BSA  $\geq 10\%$  at screening and baseline.
4. has a total PASI  $\geq 12$  at screening and baseline.
5. has a total IGA  $\geq 3$  at screening and baseline.
6. be a candidate for phototherapy or systemic treatment for plaque psoriasis.
7. must agree to avoid prolonged sun exposure and avoid use of tanning booths or other ultraviolet (UV) light sources during the study.
8. otherwise healthy on the basis of physical examination, medical history, and vital signs, and 12-lead triplicate electrocardiogram (ECG) performed at screening. Any abnormalities must be consistent with the underlying illness in the study population and this determination must be recorded in the participant's source documents and initialed by the investigator.

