### **8.2.2. Vital Signs**

Temperature, pulse/heart rate, respiratory rate, blood pressure will be assessed at every visit, as specified in the SoA (Section 1.3).

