#### **Adverse Events**

The verbatim terms used in the eCRF by investigators to identify AEs will be coded using the MedDRA. Intervention-emergent AEs are AEs with onset during the intervention period or that are a consequence of a preexisting condition that has worsened since baseline. All intervention-emergent AEs will be included in the analysis. For each AE, the percentage of participants who experience at least 1 occurrence of the given event will be summarized by intervention group. In addition, comparisons between intervention groups will be provided if appropriate.

The following analyses will also be used to assess the safety of participants in the study:

- The incidence and type of AEs.
- The incidence and type of SAEs.
- The incidence and type of severe AEs.
- The incidence and type of reasonably related AEs as assessed by the investigator.
- The incidence and type of AEs leading to discontinuation of study or study intervention.

Listings of participants with SAEs, severe AEs, AEs for psoriasis, AEs leading to discontinuation of study and anaphylactic reaction/serum sickness reactions will also be provided. All safety analyses will be based on the population of participants who received at least 1 administration of study intervention; participants will be summarized by the intervention they received.

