### 5.6. Safety Analyses

All safety analyses will be performed using safety analysis set based on actual intervention received. No formal statistical comparison is planned.

For all continuous safety variables, descriptive statistics by intervention group will include the N, mean, standard deviation, median, minimum, and maximum. Categorical variables will be summarized by intervention group using frequency counts and percentages.

The cumulative safety data will be analyzed. Unless otherwise specified, tabular summaries of safety events are also presented as following:

Safety data through Week 20 will be summarized by following intervention group:

- Placebo
- JNJ-77242113 10 mg qd CCI
- JNJ-77242113 50 mg qd CCI
- Combined JNJ-77242113 groups

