**Table 2: Clinically Important/Markedly Abnormal Vital Signs**

| Vital Sign               | Criteria   |
|--------------------------|--|
| Pulse                    | $> [120]$ bpm and with $> [30]$ bpm increase from baseline     |
|                          | $< [50]$ bpm and with $> [20]$ bpm decrease from baseline      |
| Systolic blood pressure  | $> [180]$ mm Hg and with $> [40]$ mm Hg increase from baseline |
|                          | $< [90]$ mm Hg and with $> [30]$ mm Hg decrease from baseline  |
| Diastolic blood pressure | $> [105]$ mm Hg and with $> [30]$ mm Hg increase from baseline |
|                          | $< [50]$ mm Hg and with $> [20]$ mm Hg decrease from baseline  |
| Respiratory rate         | $> [20]$ breaths per minute                                    |

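### SAP Table 2 gives respiratory rate no change-from-baseline condition, so a row labelled treatment-emergent can count values already high before dosing that never rose

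*SAP*

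**What the plan says.** SAP 5.6.3.2 plans an incidence summary and makes a table its definition: "Incidence of treatment-emergent abnormal vital signs during intervention, as defined in Table 6, will be summarized for participants who had a baseline assessment". The sentence goes on to require at least one post-baseline value for the same vital sign. The SAP has no Table 6. The only vital-sign criteria are in Table 2, directly below the sentence.

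Table 2 holds seven criteria: a high and a low one each for pulse, systolic pressure and diastolic pressure, and one for respiratory rate. The high-pulse criterion is typical of the first six: "> [120]$ bpm and with $> [30]$ bpm increase from baseline". The respiratory-rate criterion in full is "> [20]$ breaths per minute". (The stray dollar signs come from text conversion.)

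Protocol 8.2.2 confirms that the data exist: "Temperature, pulse/heart rate, respiratory rate, blood pressure will be assessed at every visit".

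**The concern.** A row labelled treatment-emergent should show abnormality that appeared or worsened after dosing started. Without a change condition, the respiratory-rate row can also include participants who were above 20 before the first dose and are above 20, but no higher, afterwards. Two programmers working from this SAP could also produce different counts, one coding the bare limit and the other inferring a baseline test. What is at stake is the accuracy of one safety row.

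**Working it through.** **1. The seven criteria, applied to an unchanged abnormal value.** The limits come from SAP Table 2.

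| Criterion | Limit | Change required | Example, no change | Counted? |
|---|---|---|---|---|
| Pulse high | > 120 | > 30 up | 125 to 125 | No |
| Pulse low | < 50 | > 20 down | 48 to 48 | No |
| Systolic high | > 180 | > 40 up | 185 to 185 | No |
| Systolic low | < 90 | > 30 down | 88 to 88 | No |
| Diastolic high | > 105 | > 30 up | 110 to 110 | No |
| Diastolic low | < 50 | > 20 down | 48 to 48 | No |
| Respiratory rate | > 20 | none | 22 to 22 | **Yes** |

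A fall in respiratory rate from 24 to 21 is counted as well.

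**2. Does another rule close the gap?**
- SAP 5.6.3.2 requires that a baseline value exist, not that it be normal.
- SAP 5.1 defines baseline, but the respiratory-rate row does not use it.
- SAP 5.6.2 defines treatment-emergent for adverse events only, by timing alone. Applied here it would confirm the miscount.
- Protocol 9.4.5 also covers adverse events only. Besides onset during the intervention period, it admits events "that are a consequence of a preexisting condition that has worsened since baseline". Applied here it would exclude 22 to 22. The two nearest rules therefore disagree.
- Inclusion criterion 8 asks that participants be "otherwise healthy on the basis of physical examination, medical history, and vital signs", and a footnote to the Schedule of Activities adds "Check clinical status again before first administration of study intervention at Week 0". Neither sets a respiratory-rate limit, so a baseline of 21 or 22 is possible.

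**3. Size, under assumptions.** The plan states no figure to reproduce and gives no respiratory-rate distribution. I therefore simulated 2,000,000 participants per scenario:
- Person mean ~ N(m, s_b). Each reading ~ N(person mean, s_w), rounded to a whole number. No drug effect.
- A screening reading, a baseline reading B, and six on-treatment readings (Weeks 1, 2, 4, 8, 12, 16) with maximum M.
- Kept only if screening is 20 or less, as a stand-in for criterion 8.
- Flagged as written: M > 20. Miscounted: M > 20 and M ≤ B. Row under the fix: M > 20 and M > B.

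| s_w | m, s_b | Flagged | Miscounted | Miscounted per 30 | Share of flags | Flags per 30: as written, then fixed |
|---|---|---|---|---|---|---|
| 1.0 | 16, 1.5 | 2.09% | 0.18% | 0.055 | 8.8% | 0.63, 0.57 |
| 1.0 | 17, 1.5 | 6.92% | 0.77% | 0.230 | 11.1% | 2.08, 1.85 |
| 1.0 | 17, 2 | 9.96% | 1.39% | 0.418 | 14.0% | 2.99, 2.57 |
| 1.0 | 18, 1.5 | 17.08% | 2.34% | 0.701 | 13.7% | 5.12, 4.42 |
| 1.5 | 16, 1.5 | 6.64% | 0.44% | 0.133 | 6.7% | 1.99, 1.86 |
| 1.5 | 17, 1.5 | 16.01% | 1.42% | 0.426 | 8.9% | 4.80, 4.38 |
| 1.5 | 17, 2 | 18.59% | 2.05% | 0.616 | 11.0% | 5.58, 4.96 |
| 1.5 | 18, 1.5 | 30.90% | 3.52% | 1.057 | 11.4% | 9.27, 8.21 |
| 2.0 | 16, 1.5 | 14.71% | 0.89% | 0.268 | 6.1% | 4.41, 4.15 |
| 2.0 | 17, 1.5 | 27.88% | 2.35% | 0.706 | 8.4% | 8.37, 7.66 |
| 2.0 | 17, 2 | 28.79% | 2.88% | 0.863 | 10.0% | 8.64, 7.77 |
| 2.0 | 18, 1.5 | 44.86% | 4.88% | 1.464 | 10.9% | 13.46, 11.99 |

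One row by hand (s_w 1.5; m 17, s_b 1.5): 0.1601 × 30 = 4.80 flags; 0.0142 × 30 = 0.43 miscounted; 1.42 / 16.01 = 8.9%; 4.80 − 0.43 = 4.37, which agrees with the 4.38 in the table within rounding.

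Across the grid the miscount is 0.055 to 1.464 per 30. For the 20-person placebo arm, multiply by 20/30: 0.04 to 0.98. Participants who start above 20 and rise further number 0.02 to 1.34 per 30. They are true worsening and are not counted as errors.

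**The case against.** The strongest reply is that the sentence above the table already supplies the test. It speaks of treatment-emergent abnormality and requires a baseline value for that vital sign; on the literal reading, that baseline value does nothing for respiratory rate. This is a fair reading, and a careful programmer may adopt it. However, the SAP makes the table the definition, and the table writes out a baseline condition for the other six criteria. The test remains unstated for the seventh.

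Three further points stand:
- **The row has little weight.** Protocol 9.4.5 plans vital-sign summaries for pulse and blood pressure only. SAP 5.6 says "No formal statistical comparison is planned".
- **The counts are assumed.** They move with the within-person SD, which is why it is varied from 1.0 to 2.0. The upper end needs a population in which 45% of participants are flagged.
- **Any increase is a weaker test than the other six rows apply.** Those require changes of more than 20 to 40 units. In the simulation, 20% to 67% of the flags left after the fix are rises of only 1 or 2 breaths.

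A reader might go further and infer that the row is mostly false flags, or that it biases the safety comparison between drug and placebo. The documents do not support either. The same rule applies to every randomized arm, and at least 86% of flags remain under the fix in every scenario tried. The missing Table 6 is a cross-reference slip and adds nothing to the point.

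**Conclusion.** The point holds, and it is minor. Coded as written, the respiratory-rate row counts participants who were above 20 before dosing and never exceeded their own baseline, which its label says it should not. The size cannot be taken from the documents. Under the assumptions above it is about 0.05 to 1.5 participants per 30-person arm, or 6% to 14% of the row's flags. It is lower if sites exclude high values at the Week 0 recheck, and zero if they exclude them all. The miscount is expected alike in all arms, and no efficacy or main safety conclusion depends on it. It would be wrong to conclude that the plan is certain to miscount, since a programmer may infer the test. The defect is that the SAP does not state it.

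**What to change.** In SAP Table 2, change the respiratory-rate row to: *more than 20 breaths per minute and with an increase from baseline* (any increase). Correct the Table 6 reference in the same edit.

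Do not require a baseline of 20 or less instead. That would drop true worsening such as 22 to 30, which the protocol's adverse-event rule would treat as emergent.

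The change is the minimum needed for the row to match its label. It does not make the row a test of marked change like the other six, and 86% to 94% of flags remain in the scenarios above.

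The cost is one table line and one derivation, made before unblinding. No new data are needed.

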**Table 2: Clinically Important/Markedly Abnormal Vital Signs**

| Vital Sign               | Criteria   |
|--------------------------|--|
| Pulse                    | $> [120]$ bpm and with $> [30]$ bpm increase from baseline     |
|                          | $< [50]$ bpm and with $> [20]$ bpm decrease from baseline      |
| Systolic blood pressure  | $> [180]$ mm Hg and with $> [40]$ mm Hg increase from baseline |
|                          | $< [90]$ mm Hg and with $> [30]$ mm Hg decrease from baseline  |
| Diastolic blood pressure | $> [105]$ mm Hg and with $> [30]$ mm Hg increase from baseline |
|                          | $< [50]$ mm Hg and with $> [20]$ mm Hg decrease from baseline  |
| Respiratory rate         | $> [20]$ breaths per minute                                    |

### 5.6.3.3. Columbia-Suicide Severity Rating Scale

The C-SSRS will be used as a screening tool to prospectively evaluate suicidal ideation and behavior among study participants. The C-SSRS measures 5 possible levels of suicidal ideation and 4 possible suicidal behaviors, as well as non-suicidal self-injurious behavior. The assessment is a fully-structured, participant self-report C-SSRS questionnaire, including standardized questions, follow-up prompts, error handling routines, and scoring conventions. Two versions of the C-SSRS will be used in this study, the *Lifetime* version and the *Since Last Contact* version. The *Lifetime* version will be conducted during the screening visit and the *Since Last Contact* version will be conducted at all other visits.

At the screening visit, the C-SSRS should be completed as the first assessment after signing informed consent and before any other tests, procedures, or other consultations. For subsequent visits, the C-SSRS should be completed after all PROs and before any other tests, procedures, or

other consultations. Participants will be interviewed by the investigator or trained study site personnel in a private, quiet place.

The following are C-SSRS categories and have binary responses (yes/no). A “yes” response to any C-SSRS category will be assigned a score as below:

**Suicidal Ideation (1-5)**

1 = Wish to be Dead

2 = Non-specific Active Suicidal Thoughts

3 = Active Suicidal Ideation with Any Methods (Not Plan) without Intent to Act

4 = Active Suicidal Ideation with Some Intent to Act, without Specific Plan

5 = Active Suicidal Ideation with Specific Plan and Intent

**Suicidal Behavior (6-10)**

6 = Preparatory Acts or Behavior

7 = Aborted Attempt

8 = Interrupted Attempt

9 = Actual Attempt (non-fatal)

10 = Completed Suicide

If no events qualify for a score of 1 to 10, a score of 0 will be assigned (0 = “Negative result [no suicidal ideation or behavior]”). Higher scores indicate greater severity.

Suicidal ideation and behavior will be summarized based on the most severe/maximum post baseline C-SSRS outcome or AE of suicidal ideation, suicidal behavior excluding completed suicide, or completed suicide through Week 20. In addition, frequency distribution of the most severe/maximum post baseline C-SSRS outcome will be tabulated by C-SSRS categories and intervention group through Week 20. The baseline is defined as the most severe/maximum C-SSRS score at either screening or Week 0.

The maximum score assigned for each participant will also be summarized into one of three broad categories: No suicidal ideation or behavior, suicidal ideation, suicidal behavior. A shift table for change in C-SSRS categories of no suicidal ideation or behavior, suicidal ideation, and suicidal behavior from baseline through Week 20 will be presented, where the baseline category is based on C-SSRS score and the post baseline is based on C-SSRS or AE data.

## 5.7. Other Analyses

### 5.7.1. Pharmacokinetics

#### 5.7.1.1. JNJ-77242113 Concentrations

The PK evaluable population is defined as all the participants who received at least 1 complete dose of JNJ-77242113 and had at least 1 valid blood sample drawn for PK analysis after their first dose of JNJ-77242113.

Plasma JNJ-77242113 concentrations will be summarized by visit and treatment group. Plasma concentration will be summarized using descriptive statistics (i.e., n, arithmetic mean, standard deviation [SD], coefficient of variation [%CV], median, range [minimum and maximum], and interquartile [IQ] range) at each visit. PK data may be displayed graphically.

The following analyses will be performed as appropriate.

- Summary of plasma JNJ-77242113 concentration over time
- Proportion of participants with plasma JNJ-77242113 concentration below the lowest quantifiable concentration in a sample at each visit
- Summary of plasma JNJ-77242113 concentrations over time by baseline body weight (quartiles). Other covariates may also be applied.
- Summary of plasma JNJ-77242113 concentrations at each visit by treatment group and baseline PASI score categories (PASI <20 or PASI ≥20)
- Plots of median plasma JNJ-77242113 concentrations over time
- Plots of median plasma JNJ-77242113 concentrations over time by baseline body weight (≤median, >median).

Concentrations below the lowest quantifiable concentration will be treated as zero in the summary statistics. All plasma concentrations below the lowest quantifiable concentration or missing data will be labeled as such in the concentration database. PK data may also be displayed graphically.

If feasible, population PK analysis of plasma concentration-time data of JNJ-77242113 may be performed using nonlinear mixed-effects modeling. Data may be combined with those of other selected studies to support a relevant structural model. Available baseline participant characteristics (eg, demographics, laboratory variables, genotypes, race) will be tested as potential covariates affecting PK parameters. Details will be given in a population PK analysis plan and the results of the population PK analysis will be presented in a separate report.

PK analysis set will be used and the analyses will be summarized through Week 16.

For the analyses, a participants included in one and only one treatment group on the basis of the treatment regimen followed. The description of treatment groups is as follows:

- JNJ-77242113 10 mg QD CCI [REDACTED]

- JNJ-77242113 50 mg QD CCI

### 5.7.1.2. Data Handling Rules

Unless otherwise specified, the following data handling rules will apply to PK sample analyses:

- Plasma concentration summaries will be based on the actual treatment received.
- All plasma concentration summaries for a particular timepoint will include data obtained from treated participants at the timepoint of interest without imputing any missing data.
- A concentration not quantifiable (below the lower limit of quantification) will be treated as 0 in the summary statistics and shown as the lower limit of quantification (< LLOQ) in the data listings.
- The data from a participant who discontinued study agent will be excluded from the by-visit data analyses from that point onwards. In addition, the data from a participant who meets 1 of the following dosing deviation criteria based on 2 previous doses prior to the PK sample collection will be excluded for that visit:
  - Skipped a visit
  - Received an incomplete/ incorrect dose

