### 1.3. Schedule of Activities (SoA)

Period	SCR	Placebo-Controlled Active Treatment							Final FU Visit a	ET b
Timeframe (Weeks)	-4 to 0	0	1	2	4	8	12	16	20	
Visit Window (Days)			(+/- 2 days)		(+/- 4 days)					
Study Procedurec										
Screening/Administrative										
Informed consent d	X									
ICF for optional biomarker substudies d	X									
Demographics	X									
Review medical history requirements	X									
Inclusion/exclusion criteria e	X	X								
Chest radiograph f	X									
IGRA g	X									
Hepatitis B and C serology	X									
HIV antibody test	X									
Serum pregnancy test h	X									
FSH i	X									
Study Intervention Administration										
Randomization		X								
Training on daily dosing diary completion j		X								
Dispense study intervention c		X			X	X	X			
Administer study intervention k			Daily self-administration							
Review daily dosing diary entries j			X	X	X	X	X	X		X
Study intervention accountability l			X	X	X	X	X	X		X
Efficacy Evaluations										
Patient-reported Outcomes (PRO)										
PSSD (7-day recall) m		X				X		X		X
DLQI m		X				X		X		X
Clinician-reported Outcomes (ClinRO)										
PASI	X	X	X	X	X	X	X	X	X	X
IGA	X	X	X	X	X	X	X	X	X	X
BSA	X	X			X	X	X	X		X
Safety Evaluations										
Full physical examination	X							X	X	X
Targeted physical examination		X	X	X	X	X	X			

Period	SCR	Placebo-Controlled Active Treatment							Final FU Visit a	ET b
Timeframe (Weeks)	-4 to 0	0	1	2	4	8	12	16	20	
Visit Window (Days)			(+/- 2 days)		(+/- 4 days)					
Study Procedurec										
Height	X									
Weight	X	X						X		X
Vital signs n	X	X	X	X	X	X	X	X	X	X
Tuberculosis evaluation o	X	X	X	X	X	X	X	X	X	X
12-lead ECG p	X	X	X					X		X
C-SSRS q	X	X	X	X	X	X	X	X	X	X
Urine pregnancy test h		X	X	X	X	X	X	X	X	X
Clinical Laboratory Testsr										
Hematology	X	X	X		X	X	X	X	X	X
Chemistry	X	X	X		X	X	X	X	X	X
Lipid panel s	X	X						X		X
hs-CRP		X				X		X		X
Urinalysis t	X	X	X		X	X	X	X	X	X
Clinical Pharmacology Assessmentsr										
JNJ-77242113 plasma concentrations		X	X	X	X	X	X	X	X	X
Serum Antibodies to JNJ-77242113 (ADA)		X		X	X	X		X	X	X

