### **Clinical Studies**

A Phase 1, first-in-human (FIH), randomized, double-blind, placebo-controlled study (PN- 235- 01) of single and multiple ascending doses of JNJ-77242113 in healthy participants was completed by Protagonist Therapeutics, Inc. to assess the safety, tolerability, and PK of JNJ- 77242113 over the dose range of 10 mg to 1,000 mg and formulations tested (ie, oral solution and delayed release tablet). The SAD part (Part 1) consisted of 5 cohorts (doses: 10 mg, 25 mg, 100 mg, 300 mg, and 1,000 mg) of 8 participants each (nominal n=6 active, n=2 placebo per cohort). The MAD part (Part 2) consisted of 5 cohorts (doses: 10 mg, 25 mg, 100 mg, 300 mg, and 1,000 mg once daily for 10 days) with up to 10 participants each (nominal n=8 active, n=2 placebo). Part 3 of this study consisted of 12 participants who received single doses of 25 mg JNJ-77242113 in a randomized, open-label, 4-way crossover fashion to assess the bioavailability and PK of delayed release oral tablet formulations CCI relative to the oral solution formulation used in Parts 1 and 2. Part 3 also evaluated the food effect for the delayed release tablet formulation CCI. Results from Part 3 indicated that the JNJ-77242113 with CCI

CCI relative to the oral solution. The JNJ-77242113 CCI to the oral solution, but this CCI was less pronounced than the results observed for CCI conditions. Systemic exposure ( $C_{\max}$  and AUC) to the drug is approximately dose- proportional across the dose range evaluated. After multiple once daily dosing steady-state was achieved by Day 7, consistent with the observed mean terminal phase half-life of approximately 9 to 12 hours. After multiple once daily dosing minimal accumulation was observed, consistent with the half-life. A summary of the PK from the SAD and MAD FIH study can be found in the IB.

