### 5.7.1.3. PK vs Efficacy

To explore the relationship between JNJ-77242113 plasma concentrations and efficacy endpoints, the following analyses may be explored:

- The relationship between JNJ-77242113 plasma concentrations (quartiles) and PASI 75 response and IGA 0/1 response at Week 16 may be explored.

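### The SAP's rule for excluding PK samples after a dosing deviation is keyed to skipped visits, so read literally it keeps samples taken after a missed home-taken evening tablet

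*SAP*

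**What the plan says.** SAP 5.7.1.2 removes PK data from the by-visit analyses in two situations. One is discontinuation of study agent, from that point on. The other is that participants who meet one of the "dosing deviation criteria based on 2 previous doses prior to the PK sample collection will be excluded for that visit". The two criteria are "Skipped a visit" and "Received an incomplete/ incorrect dose". Neither names a dose that was not taken.

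After the observed first dose at Week 0, the Protocol's Schedule of Activities (1.3) gives dosing as "Daily self-administration". Protocol 6.1 places it in the evening, and visits are 1 to 4 weeks apart. On the diary, the Schedule's footnotes state: "Participants will be instructed to complete a daily dosing diary to record the date and time of the following"; the items listed include when the tablet is taken.

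The retained concentrations feed the by-visit summaries and the below-quantification proportions in SAP 5.7.1.1. They also feed SAP 5.7.1.3, which reads: "The relationship between JNJ-77242113 plasma concentrations (quartiles) and PASI 75 response and IGA 0/1 response at Week 16 may be explored".

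**The concern.** The two-dose look-back shows what the rule is for: to remove concentrations that do not reflect the assigned regimen because a recent dose went wrong. The skipped-visit trigger suits a drug given at visits. In this trial the two previous doses are the two preceding evenings, and attending the clinic says nothing about whether those tablets were taken. A visit that was skipped leaves no sample to exclude. If the trigger is read as an earlier skipped visit, it could drop valid samples from adherent participants.

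That leaves the second trigger to catch an untaken tablet, and its verb is about a dose received. Two programmers could build different PK datasets from this text. On the literal reading, low values caused by non-adherence are summarised as exposure at the assigned dose. Values below quantification enter as zero. In the quartile analysis, a missed tablet can move a participant into a low-exposure quartile for a reason unrelated to usual exposure over 16 weeks.

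**Working it through.** **Does the text cover a missed tablet?** SAP Appendix 4 has a deviation category for wrong treatment or incorrect dose, and asks separately for a listing of patients who missed scheduled administrations. SAP Appendix 7 likewise names incorrect agent or dose received and missed administrations as two things. By the SAP's own usage, a missed tablet is not clearly an incomplete or incorrect dose received.

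**Inputs**
- Half-life: Protocol 2.2 (Clinical Studies) gives an "observed mean terminal phase half-life of approximately 9 to 12 hours", from the first-in-human study in healthy participants.
- Dosing interval: 24 h (Protocol 6.1). Doses 10 mg and 50 mg, a 5-fold ratio.
- Exposure approximately proportional to dose (Protocol 4.3).
- 30 participants per active arm (Protocol 9.2).
- Miss rate: not given. Range assumed: 5% to 20%. Protocol 6.4 calls a participant noncompliant above 20% missed over the study.

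The plan states no figure to reproduce. As a check on the inputs, let f = 2^(−24/t½) be the fraction left after one dosing interval. The accumulation ratio 1/(1 − f) is 1.19 at 9 h and 1.33 at 12 h, which agrees with the minimal accumulation reported in Protocol 2.2.

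**Effect on one sample** (steady state, log-linear decline)

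| Doses missed before the sample | Formula | t½ 9 h | t½ 12 h |
|---|---|---|---|
| Last dose only | f | 15.7% | 25.0% |
| Both of the last two | f² | 2.5% | 6.25% |
| Second-last only | 1 − f(1 − f) | 86.7% | 81.25% |

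For a 50 mg participant, missing the last dose gives 50 × 0.157 = 7.9 mg-equivalent to 50 × 0.25 = 12.5 mg-equivalent, which brackets 10 mg. Missing both gives 1.2 to 3.1 mg-equivalent. Missing only the second-last has little effect.

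**How often, per arm and visit**
- Last dose missed: 30 × 0.05 = 1.5 to 30 × 0.20 = 6.0 samples.
- At least one sample affected: 1 − 0.95³⁰ = 0.79 at 5%; above 0.99 at 20%.
- At least one of the last two missed, with independent misses: 30 × (1 − 0.95²) = 2.9 to 30 × (1 − 0.80²) = 10.8.

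**Effect on the 50 mg arithmetic mean** (last dose only): the mean is multiplied by 1 − m(1 − f), where m is the miss rate. At m = 5% the fall is 3.8% to 4.2%; at m = 20% it is 15% to 17%.

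**The case against.** The strongest reply is that the second trigger already covers the case. Under a lead-in about dosing deviations in the two previous doses, zero tablets can be read as an incomplete dose. That reading is possible, but Appendices 4 and 7 point the other way. The text should settle it.

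Second, time since dose is already handled elsewhere. Protocol 8.4.3 derives PK parameters and exposure by population PK from actual doses and actual sampling times, and SAP 5.7.1.1 also describes population PK. This stands: exposure derived that way does not depend on the by-visit exclusion. It is conditional on feasibility, however, and SAP 5.7.1.3 specifies plasma concentrations.

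Third, the magnitude rests on borrowed inputs. The half-life comes from healthy participants, and the ascending-dose parts of that study used an oral solution; here a delayed-release tablet is given to patients with psoriasis. The 20% is a per-participant threshold, so applying it to a whole arm is an extreme case. Both caveats stand.

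A reader might go further and infer that the rule blurs the 10 mg and 50 mg arms or undermines the efficacy result. The documents do not support that. The affected participant remains in the 50 mg group. The arm mean falls by about 4% to 17% over the assumed range. If both arms miss doses at the same rate, the factor 1 − m(1 − f) cancels and the ratio of means is unchanged. The SAP also reports medians and interquartile ranges, which are less sensitive to a few low values. The by-visit outputs are descriptive, and no efficacy test uses this rule.

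**Conclusion.** The point holds as a wrongly specified handling rule with limited reach. Followed literally, SAP 5.7.1.2 retains samples it is meant to remove; read generously, it is ambiguous. For an affected individual the distortion is large: about one sixth to one quarter of the expected concentration, so that a 50 mg participant's value resembles one from 8 to 12.5 mg. This assumes that the healthy-participant half-life carries over, that decline is log-linear and that exposure is dose-proportional. How many samples are affected depends on an adherence rate the documents do not give.

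The consequence is confined to exploratory by-visit concentration summaries, below-quantification proportions and an optional quartile analysis. The primary PASI 75 analysis is untouched. The correction is worth making because it costs little and serves the rule's own purpose.

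**What to change.** In SAP 5.7.1.2:
- Replace the skipped-visit trigger with: the last scheduled dose before the sample was not taken, per the daily dosing diary checked against tablet counts. The cross-check matters because a blank diary entry is not proof of a missed dose, and Protocol 6.4 assesses compliance by counting returned tablets.
- Keep the incomplete or incorrect dose criterion.
- Flag, but retain, samples where only the second-last dose was missed, since 81% to 87% of the expected level remains.
- List all excluded samples.

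In SAP 5.7.1.3, form the quartiles from population-PK exposure where it is available. Otherwise apply the same exclusion and report time since last dose.

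This changes SAP wording only; dose and sample times are already collected. The cost is about 1.5 to 6 of 30 samples per arm and visit at assumed miss rates of 5% to 20%. Excluding for a miss of any of the last two doses would cost 2.9 to 10.8 of 30 and would discard many samples that are barely affected, so the last dose is the better trigger.
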